Change in Sponsor's Protocol Lead	Signature Page – Protocol Lead	83	
PPD [REDACTED]
 
EMD Serono Research & Development Institute, Inc. [name] Telephone number: PPD [REDACTED] Fax number: PPD [REDACTED] PPD [REDACTED]
	
PPD [REDACTED]
 
PPD [REDACTED]
 
EMD Serono Research & Development Institute, Inc. [name] Telephone number: PPD [REDACTED] [REDACTED] Fax number: PPD [REDACTED]

Change	Section	Page	Previous Wording	New Wording
				PPD [REDACTED]
Change in Sponsor's PPD [REDACTED]	Sponsor Responsible Persons	87	PPD [REDACTED] EMD Serono Research and Development Institute, Inc. [name] PPD [REDACTED] PPD [REDACTED] PPD [REDACTED]	PPD [REDACTED] PPD [REDACTED] EMD Serono Research and Development Institute, Inc. [name] PPD [REDACTED] PPD [REDACTED]
Change in Sponsor's PPD [REDACTED]	Sponsor Responsible Persons	87	PPD [REDACTED] EMD Serono Research and Development Institute, Inc. [name] PPD [REDACTED] PPD [REDACTED]	PPD [REDACTED] PPD [REDACTED] EMD Serono Research and Development Institute, Inc. [name] PPD [REDACTED] PPD [REDACTED]

Amendment 5 – Table 1 Schedule of Assessments – Screening through Week 52

Trial Period	Screening	Weeks During Double-blind Treatment Period (Visit Window ±3 days)																		
		0		2	3	4	8	12	16	20	24	28	32	36	40	44	48	52		
Trial Day	-28 -42 to -1	1	3	5	15	22	29	57	85	113	141	169	197	225	253	281	309	337	365	
Informed consent	X																			
Inclusion/exclusion criteria	X	X ^a																		
CCI																				
Pharmacokinetic informed consent (Rich PK sampling only)	X																			
Demographic data	X																			
SSc-ILD and other medical history, medications, surgery/procedures	X																			
HRCT	X											X								X
12-lead ECG (locally read)	X											X								X
Tuberculosis assessment	X																			
Serum virology (HIV, HCV, HBV)	X																			
Serum pregnancy test ^c	X																			
PT, aPTT, TSH, and NT pro-BNP	X																			
Urine pregnancy test ^{c,d}		X					X	X	X	X	X	X	X	X	X	X	X	X	X	X
Physical examination	X	X			X ^e		X	X ^e	X ^e	X ^e	X ^e	X	X ^e	X ^e	X ^e	X ^e	X ^e	X ^e	X ^e	X

Trial Period	Screening	Weeks During Double-blind Treatment Period (Visit Window ± 3 days)																	
		0			2	3	4	8	12	16	20	24	28	32	36	40	44	48	52
Trial Day	-28-42 to -1	1	3	5	15	22	29	57	85	113	141	169	197	225	253	281	309	337	365
Vital signs, weight, height ^f	X	X			X		X	X	X	X	X	X	X	X	X	X	X	X	X
Mahler BDI/TDI and SGRQ ^g		X							X			X			X				X
Patient's Global Assessment, Leicester Cough Index, SHAQ, EQ-5D, and Physician's Global Assessment ^g		X										X							X
Randomization		X																	
IMP administration		X					X	X	X	X	X	X	X	X	X	X	X	X	X
PK sampling ^h		X					X	X		X									
Rich PK sampling ⁱ			X	X	X	X													
Routine hematology, clinical chemistry, urinalysis dipstick ^j	X	X			X		X	X	X	X	X	X		X	X	X		X	X
Pulmonary function tests (FVC, TLC) with DLCO ^k	X	X							X			X			X				X
mRSS		X							X			X			X				X
Digital ulcer counts ^l		X							X			X			X				X
Serum for ADA		X										X							X
Sample for autoantibodies		X										X							X

Trial Period	Screening	Weeks During Double-blind Treatment Period (Visit Window ± 3 days)																	
Week		0			2	3	4	8	12	16	20	24	28	32	36	40	44	48	52
Trial Day	-28 -42 to -1	1	3	5	15	22	29	57	85	113	141	169	197	225	253	281	309	337	365
Concomitant medications/procedures	X	X			X		X	X	X	X	X	X	X	X	X	X	X	X	X
Adverse events ^{no}	X	X			X		X	X	X	X	X	X	X	X	X	X	X	X	X

CCI

ADA = antidrug antibodies; AE = adverse event; aPTT = activated partial thromboplastin time; BDI = Baseline Dyspnea Index; DLCO = diffusion capacity of the lung for carbon monoxide; ECG = electrocardiogram; FVC = forced vital capacity; HBV = hepatitis B virus; HCV = hepatitis C virus; HIV = human immunodeficiency virus; HRCT = high-resolution computed tomography; IMP = investigational medicinal product; mRSS = modified Rodnan skin score; PK = pharmacokinetic; PT = prothrombin time; SGRQ = St. George Respiratory Questionnaire; SHAQ = Scleroderma Health Assessment Questionnaire; SSc-ILC = systemic sclerosis-associated interstitial lung disease; TDI = Transition Dyspnea Index; ~~TLC = total lung capacity~~; TSH = thyroid-stimulating hormone; VAS = visual analog scale.

a Subject eligibility (based on screening assessments of the inclusion and exclusion criteria) must be checked again on Day 1 prior to randomization.

CCI

- c For women of childbearing potential or who are postmenopausal for less than 2 years. At Day 1, if the urine test is negative, the subject can be randomized and receive the first dose of IMP.
- d Performed locally per local constraints and regulations.
- e Focused physical examination only, according to standard of care.
- f Vital signs include 10-minute seated arterial blood pressure, pulse rate, and body temperature. Height will be measured at Day 1 only. Weight will be measured at Weeks 0, 24, 52, 76, and 104. Body weight will be measured with a balance beam scale, if possible.
- g Questionnaires should be completed before any other procedures are performed. Questionnaires should be performed in the following order: Patient's Global Assessment, SHAQ, Mahler BDI (at Day 1) followed by Mahler TDI at the subsequent visits, SGRQ, Leicester Cough Index, and EQ-5D. The Mahler BDI/TDI administrator must be blinded to other assessments. The Physician's Global Assessment (VAS) may be performed after other assessments at the visit are completed.
- h For all subjects, samples will be collected predose and immediately after the end of IMP infusion at Weeks 0 (Day 1), 4, 8, and 16.
- i For subjects who have provided informed consent for the rich PK sampling, additional samples will be collected on Days 3, 5, 15, and 22 (in addition to the pre- and postdose samples at Weeks 0, 4, 8, and 16; see footnote h).
- j See Section 7.4.3 for list of routine laboratory assessments. Urine protein:creatinine ratio to be performed if dipstick urinalysis reveals at least 3+ protein. Microscopic urinalysis to be performed if blood is present.
- k ~~The TLC should be performed at Weeks 0, 24, 52, 76, and 104.~~ The DLCO measurements will be corrected for hemoglobin level, and spirometry assessments will be centrally adjudicated.
- l Digital ulcers are those distal to the metacarpal phalangeal joints. New or worsening digital ulcers, or at any other site on the body, will be captured as AEs.

CCI

CCI

Adverse events should also be assessed for occurrence during the periods between trial visits.

Amendment 5 – Table 2 Schedule of Assessments – Week 56 through Safety Follow-up

Trial Period	Weeks During Double-blind Treatment Period (Visit Window ±5 days)													ET ^a	Safety Follow-up Number weeks post last visit (±5 days)		Survival Follow-up Post Last Trial Visit
	56	60	64	68	72	76	80	84	88	92	96	100	104		4	12	Every 12 Weeks
Trial Day	393	421	449	477	505	533	561	589	617	645	673	701	729				
HRCT													X	X			
12-lead ECG (locally read)						X							X	X		X	
Urine pregnancy test ^{b,c}	X	X	X	X	X	X	X	X	X	X	X	X	X	X	X	X	
Physical examination	X ^d	X ^d	X ^d	X ^d	X ^d	X	X ^d	X ^d	X ^d	X ^d	X ^d	X ^d	X	X	X ^d	X	
Vital signs, weight ^e	X	X	X	X	X	X	X	X	X	X	X	X	X	X	X	X	
Mahler TDI and SGRQ ^f			X			X			X				X	X		X	
Patient's Global Assessment, Leicester Cough Index, SHAQ, EQ-5D, and Physician's Global Assessment ^f						X							X	X			
IMP administration	X	X	X	X	X	X	X	X	X	X	X	X					
Routine hematology, clinical chemistry, urinalysis ^g		X	X	X		X		X	X	X		X	X	X	X	X	
Pulmonary function tests (FVC, TLC) with DLCO ^h			X			X			X				X	X		X	
mRSS			X			X			X				X	X		X	
Digital ulcer counts ⁱ			X			X			X				X	X		X	
Serum for ADA						X							X	X	X	X	
Sample for autoantibodies													X	X			
CCI																	
Concomitant medications/procedures	X	X	X	X	X	X	X	X	X	X	X	X	X	X	X	X	

Trial Period	Weeks During Double-blind Treatment Period (Visit Window ± 5 days)													ET ^a	Safety Follow-up Number weeks post last visit (± 5 days)		Survival Follow-up Post Last Trial Visit
	56	60	64	68	72	76	80	84	88	92	96	100	104		4	12	Every 12 Weeks
Week																	
Trial Day	393	421	449	477	505	533	561	589	617	645	673	701	729				
Adverse events ^j	X	X	X	X	X	X	X	X	X	X	X	X	X	X	X	X	
Vital status ^k																	X

ADA = antidrug antibodies; AE = adverse event; BDI = Baseline Dyspnea Index; DLCO = diffusion capacity of the lung for carbon monoxide; ECG = electrocardiogram; ET = early termination; FVC = forced vital capacity; HRCT = high resolution computed tomography; IMP = investigational medicinal product; mRSS = modified Rodnan skin score; SGRQ = St. George Respiratory Questionnaire; SHAQ = Scleroderma Health Assessment Questionnaire; TDI = Transition Dyspnea Index; TLC = total lung capacity; VAS = visual analog scale.

- a Subjects who discontinue IMP for any reason should complete the ET visit as soon as possible, but within 2 weeks of IMP discontinuation, and then the remaining scheduled trial visits. At a minimum, the subject is expected to complete the trial visits at Weeks 12, 24, 36, 52, 64, 76, 88, and 104, as well as the Safety Follow-up period Week 12 visit. Subjects with discontinued IMP can come to the other scheduled visits during the trial period according to the Investigator's judgment. Subjects who withdraw from the treatment period would have an early termination visit followed by entrance into the Safety Follow-up Period. Subjects who withdraw from the trial (eg, withdraw consent, lost to follow up, or death; see Section 5.5.2) would not have any additional trial visits. All subjects will be followed up by the site approximately every 12 weeks for survival from the subject's last trial visit until death or the end of the trial.
- b For women of childbearing potential or who are postmenopausal for less than 2 years. Positive urine pregnancy tests should be confirmed with a serum test. If the serum pregnancy test is subsequently positive, the subject will be withdrawn from IMP.
- c Performed locally per local constraints and regulations.
- d Focused physical examination only, according to standard of care.
- e Vital signs include 10-minute seated arterial blood pressure, pulse rate, and body temperature. Weight will be measured at Weeks 0, 24, 52, 76, and 104. Body weight will be measured with a balance beam scale, if possible.
- f Questionnaires should be completed before any other procedures are performed. Questionnaires should be performed in the following order: Patient's Global Assessment, SHAQ, Mahler BDI (at Day 1) followed by Mahler TDI at the subsequent visits, SGRQ, Leicester Cough Index, and EQ-5D. The Mahler BDI/TDI administrator must be blinded to other assessments. The Physician's Global Assessment (VAS) may be performed after other assessments at the visit are completed.
- g See Section 7.4.3 for list of routine laboratory assessments. Urine protein:creatinine ratio to be performed if dipstick urinalysis reveals at least 3+ protein. Microscopic urinalysis to be performed if blood is present.
- h The TLC should be performed at Weeks 0, 24, 52, 76, and 104. The DLCO measurements will be corrected for hemoglobin level, and spirometry assessments will be centrally adjudicated.
- i Digital ulcers are those distal to the metacarpal phalangeal joints. New or worsening digital ulcers, or at any other site on the body, will be captured as AEs.
- j Adverse events should also be assessed for occurrence during the periods between trial visits.
- k Survival follow-up: All subjects will be assessed for survival every 12 weeks (± 1 week) from the last trial visit until death or end of the trial.

Listing 16.2.9.1: Vital Signs – SAF Analysis Set.....81
Listing 16.2.9.2: Electrocardiogram Data – SAF Analysis Set82

3 List of Abbreviations and Definition of Terms

Refer to the Study SAP.

4 Modification History

Unique Identifier for SAP Version	Date of SAP Version	Author	Changes from the Previous Version
1.0	05 April 2018	PPD	N/A – First version

5 Purpose of the Statistical Analysis Plan Addendum

The purpose of this statistical analysis plan (SAP) addendum is to document technical and detailed specifications for the Final Analysis for protocol EMR200017-014.

Due to the early termination of the study and consequently the limited number of subjects and data available, the full pre-planned analyses in the Study SAP (dated 15 November 2017) will not be carried out, since they may lead to unreliable conclusions. Hence this addendum references the applicable parts of the Study SAP and the Independent Data Monitoring Committee (IDMC) SAP (dated 29 June 2016) to produce the tables, listings, and figures (TLFs) to be included in the abbreviated clinical study report (CSR).

6 Summary of Clinical Study Features

Refer to the Study SAP.

7 Sample Size/Randomization

Refer to the Study SAP.

8 Overview of Planned Analyses

8.1 Final Analysis

Cut-off date:

The data cut-off date for the final analysis will be when all randomized subjects have completed the Week 12 Safety Follow-up visit or been lost to follow-up. No more data are expected to be entered into the database by the sites after this point.

A blinded data review meeting will be held prior to database lock in order to identify and confirm protocol deviations (PDs).

Dissemination of results:

The blinded Biostatistics study team will become unblinded after database lock. Results will be generated on the aggregate group level and delivered to the Sponsor as one package (no key TLFs will be produced) following the normal process.

TLF Shells:

Refer to [Appendix 1](#) for the TLF shells.

9 Changes to the Planned Analyses in the Clinical Study Protocol

See subsequent sections regarding the analyses that will be performed for the abbreviated CSR.

10 Protocol Deviations and Analysis Sets

Refer to the Study SAP.

Subject disposition will use the Screening Analysis Set, all baseline and safety summaries will use the Safety Analysis Set and all efficacy summaries will use the mITT Analysis Set. The other analysis sets will not be required for the following reasons:

- Intent-to-treat – All randomized subjects were treated so this is equivalent to the mITT analysis set.
- Per-Protocol – The purpose of this was for sensitivity analysis on the primary and key secondary endpoints, which will no longer be performed.
- PK – No PK analyses will be performed for the abbreviated CSR.
- Pharmacogenetics – No CC1 analyses will be performed for the abbreviated CSR.

Since no supportive analyses on the primary endpoint will be performed, no subgroups will be identified.

11 General Specifications for Statistical Analyses

Refer to the Study SAP. Only summary statistics will be computed.

Early Termination Visit:

Since subjects will be performing their early termination (ET) visits at different stages within the protocol schedule of assessments, for the efficacy by-visit summaries, the ET visits will reference the protocol visits in between which they fell chronologically.

For example, if a subject performed their Week 12 visit, then performed their ET visit at a later date (but before their scheduled Week 24 visit), their ET visit will be shown as “ET (W12 – W24)” to display the weeks that it fell between.

Missing data:

No imputation of missing efficacy data or duration of prior mycophenolate use at baseline will be performed.

12 Study Subjects

Subject disposition status will be summarized as per the Study SAP. Important PDs will be listed only and clinically important PDs will not be identified.

13 Demographics and Other Baseline Characteristics

Demographics, medical history, and disease history will be summarized as per the IDMC SAP.

14 Previous or Concomitant Medications/Procedures

Previous and concomitant medications will be summarized as per the IDMC SAP.

15 Treatment Compliance and Exposure

The following will be summarized using descriptive statistics:

- Treatment duration (weeks)
- Number of infusions of trial treatment received
- Treatment adherence (%)
- Infusion duration (hours) and volume (mL)
- Number of subjects with at least one dose adjustment (overall and by reason)
- Number of subjects with at least one infusion not completed as planned (overall and by reason)

Refer to the Study SAP for definitions.

16 Endpoint Evaluation

Summary statistics of absolute values and change from baseline will be provided for the following efficacy measurements. No statistical tests will be performed or confidence intervals presented.

Pulmonary function tests:

- FVC
- FVC % Predicted
- DLCO – eCRF result
- DLCO % Predicted – eCRF result
- KCO – eCRF result

HRCT results:

- QLF
- Total ILD

QoL questionnaires:

- Mahler TDI
- SGRQ
- Physician’s Global Assessment
- Patient’s Global Assessment
- SHAQ – VAS scores only
- EQ-5D – VAS score only

- Leicester Cough Index

Skin fibrosis:

- mRSS
- Digital Ulcer Count

Clinically meaningful disease progression and overall survival:

- Disease Progression
- Listing of Deaths

Refer to the Study SAP for details of these measurements and any derivations required.

17 Safety Evaluation

Refer to the IDMC SAP for the safety summaries that will be provided.

18 Appendix 1 – TLF shells

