- f Vital signs include 10-minute seated arterial blood pressure, pulse rate, and body temperature. Height will be measured at Day 1 only. Weight will be measured at Weeks 0, 24, 52, 76, and 104. Body weight will be measured with a balance beam scale, if possible.
- g Questionnaires should be completed before any other procedures are performed. Questionnaires should be performed in the following order: Patient's Global Assessment, SHAQ, Mahler BDI (at Day 1) followed by Mahler TDI at the subsequent visits, SGRQ, Leicester Cough Index, and EQ-5D. The Mahler BDI/TDI administrator must be blinded to other assessments. The Physician's Global Assessment (VAS) may be performed after other assessments at the visit are completed.
- h For all subjects, samples will be collected predose and immediately after the end of IMP infusion at Weeks 0 (Day 1), 4, 8, and 16.
- i For subjects who have provided informed consent for the rich PK sampling, additional samples will be collected on Days 3, 5, 15, and 22 (in addition to the pre- and postdose samples at Weeks 0, 4, 8, and 16; see footnote h).
- j See Section 7.4.3 for list of routine laboratory assessments. Urine protein:creatinine ratio to be performed if dipstick urinalysis reveals at least 3+ protein. Microscopic urinalysis to be performed if blood is present.
- k The DLCO measurements will be corrected for hemoglobin level, and spirometry assessments will be centrally adjudicated.
- l Digital ulcers are those distal to the metacarpal phalangeal joints. New or worsening digital ulcers, or at any other site on the body, will be captured as AEs.

CCI

CCI

- o Adverse events should also be assessed for occurrence during the periods between trial visits.

Table 2 Schedule of Assessments – Week 56 through Safety Follow-up

Trial Period	Weeks During Double-blind Treatment Period (Visit Window ±5 days)													ET ^a	Safety Follow-up Number weeks post last visit (±5 days)		Survival Follow-up Post Last Trial Visit
	56	60	64	68	72	76	80	84	88	92	96	100	104		4	12	
Week	393	421	449	477	505	533	561	589	617	645	673	701	729				
Trial Day	393	421	449	477	505	533	561	589	617	645	673	701	729				
HRCT													X	X			
12-lead ECG (locally read)						X							X	X		X	
Urine pregnancy test ^{b,c}	X	X	X	X	X	X	X	X	X	X	X	X	X	X	X	X	
Physical examination	X ^d	X ^d	X ^d	X ^d	X ^d	X	X ^d	X ^d	X ^d	X ^d	X ^d	X ^d	X	X	X ^d	X	
Vital signs, weight ^e	X	X	X	X	X	X	X	X	X	X	X	X	X	X	X	X	
Mahler TDI and SGRQ ^f			X			X			X				X	X		X	

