5.3.2 Exclusion Criteria

Subjects are not eligible for this trial if they fulfill any of the following exclusion criteria:

1. Any condition that in the Investigator's opinion constitutes an inappropriate risk or a contraindication for participation in the trial or that could interfere with the trial objectives, conduct, or evaluation.
2. Renal impairment (glomerular filtration rate [GFR] < 45 mL/min/1.73 m² as calculated by the Modification of Diet in Renal Disease equation) calculated by the central laboratory as follows:

$$\text{GFR (mL/min per 1.73 m}^2\text{)} = 175 \times \text{standardized serum creatinine}^{-1.154} \times \text{age}^{-0.203} \times 1.212$$

(if black) \times 0.742 (if female)

3. Urine dipstick with $\geq 3+$ protein and urine protein:creatinine ratio > 2 mg/mg. Urine protein:creatinine ratio will be determined only if urine dipstick indicates $\geq 3+$ protein.
4. Known diagnosis of obstructive lung disease/emphysema as defined by forced expiratory volume in 1 second (FEV₁)/FVC ratio < 0.65 and/or significant emphysematous change on screening HRCT according to the central reader.
5. Other clinically significant abnormalities on HRCT not attributable to scleroderma or emphysema as defined above, which in the Investigator's opinion make enrollment in the trial inappropriate.
6. Known diagnosis of other significant respiratory disorders in the opinion of the Investigator.
7. Pulmonary hypertension that fulfills at least one of the following:
 - Currently being treated with systemic therapy targeted to PAH or pulmonary hypertension;
 - Considered by the Investigator to require initiation of systemic targeted PAH therapy;
 - History of transthoracic echocardiography showing at least one of the following (unless right heart catheterization subsequent to these measures did not reveal pulmonary hypertension): tricuspid regurgitation jet > 2.8 m/sec, right atrial enlargement (major dimension > 53 mm), right ventricular enlargement (mid cavity dimension > 35 mm), moderate to severe left ventricular dysfunction;
 - At screening, N-terminal prohormone brain natriuretic peptide (NT pro-BNP) $> 3 \times$ the upper limit of normal (ULN), unless, for example, right heart catheterization performed within 3 months of the Screening Visit did not reveal pulmonary hypertension.

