6.5.4 Special Precautions

Abituzumab may have adverse effects common to monoclonal antibodies as well as compounds with anti-integrin activity and antiangiogenic potential.

CCI

For women who are not postmenopausal (≥ 12 months of non-therapy-induced amenorrhea) or surgically sterile (absence of ovaries and/or uterus): agreement to remain abstinent or use two effective methods of contraception, including at least one highly effective method that can achieve a failure rate of < 1% per year, when used consistently and correctly, and one other reliable method during the treatment period and for at least 90 days after the last dose of study treatment.

Examples of contraceptive methods with a failure rate of < 1% per year (highly effective contraceptive methods) include:

- combined (estrogen and progesterone containing) hormonal contraception associated with inhibition of ovulation¹ (oral, intravaginal, transdermal)
- progesterone-only hormonal contraception associated with inhibition of ovulation¹ (oral, injectable, implantable²)
- IUD²
- IUS²
- bilateral tubal occlusion²
- vasectomized partner^{2,3}
- sexual abstinence⁴

¹ Hormonal contraception may be susceptible to interaction with the IMP, which may reduce the efficacy of the contraception method.

² Contraception methods in the context of this guidance are considered to have low user dependency.

³ Vasectomized partner is a highly effective birth control method provided that the partner is the sole sexual partner of the woman of childbearing potential trial participant and that the vasectomized partner has received medical assessment of the surgical success.

⁴ In the context of this guidance, sexual abstinence is considered a highly effective method only if defined as refraining from heterosexual intercourse during the entire period of risk associated with the study treatments. The reliability of sexual abstinence needs to be evaluated in relation to the duration of the clinical trial and the preferred and usual lifestyle of the subject.

Barrier methods supplemented with the use of a spermicide could be considered as a reliable method.

For men (including those who have undergone a vasectomy): agreement to remain abstinent or use a condom during the treatment period and for at least 12 months after the last dose of study treatment and agreement to refrain from donating sperm during this same period.

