8.3.3 Safety Endpoints

Safety endpoints in this trial include the following:

- The nature, incidence, severity, relationship, and outcome of AEs, SAEs, and AESIs from screening up to Week 116;
- Number of subjects with treatment-emergent AEs, SAEs, and AESIs from baseline up to Week 116;
- Treatment-emergent changes in clinical laboratory measures, ECGs, and vital signs from baseline up to Week 116;
- Incidence of subjects with positive ADA titers from baseline up to Week 116.

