8.5.3 Analysis of Secondary Endpoints

Analysis of Key Secondary Efficacy Endpoints

The key secondary endpoints will be tested for abituzumab 1500 mg versus placebo, using data for subjects on trial treatment, in the following order after the primary endpoint is met.

1. The Mahler TDI at Week 52 will be analyzed using a mixed-effects model adjusting for baseline FVC% predicted, duration of prior mycophenolate use at baseline, and Mahler BDI.
2. The absolute change in SGRQ total score at Week 52 will be analyzed using a mixed-effects model adjusting for baseline FVC% predicted, duration of prior mycophenolate use at baseline, and baseline SGRQ score.
3. The absolute change from baseline in mRSS at Week 52 in subjects with dcSSc at baseline will be analyzed using a mixed-effects model adjusting for baseline FVC% predicted, duration of prior mycophenolate use at baseline, and baseline mRSS.
4. The absolute change from baseline in QLF in the region of highest severity at Week 52 will be analyzed using an ANCOVA model adjusting for baseline FVC% predicted, duration of prior mycophenolate use at baseline, and baseline QLF.
5. Overall survival will be analyzed using a stratified log-rank test and presented by Kaplan-Meier estimates and 95% confidence interval, including the survival data available up to the analysis cut-off date. A Cox proportional hazards regression model will be used to obtain hazard ratios and 95% confidence intervals adjusting for baseline FVC% predicted and duration of prior mycophenolate use at baseline.

The mixed-effects model will include random intercept, treatment, and visit as fixed effect terms, treatment-by-visit as the interaction term, adjusting for baseline covariates. An unstructured covariance matrix will be used as the default option. Missing data is assumed MAR.

Missing data for binary endpoint will be imputed as non-responders.

Analysis of Other Secondary Efficacy Endpoints

CCI [REDACTED]

[REDACTED]

[REDACTED]

Analysis of Safety Endpoints

Adverse events will be summarized by treatment group, by severity, and by relationship to IMP. Serious AEs, AEs leading to treatment discontinuation, and AESI will be summarized by treatment group.

Summary statistics will be used to present changes from baseline in continuous laboratory and vital sign data. Shift tables will be used to present changes in categorical laboratory parameters. Figures may be generated to assist safety evaluation.

Analysis of Quality of Life Endpoints

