16.2.7: Display of Adverse Events
Listing 16.2.7.3: Listing of Deaths - SAF Analysis Set

Treatment Group	Subject Identifier	Informed Consent Date	Randomization Date	First/Last Trial Trt. Date	Death Date (days since last dose)	Primary Reason for Death
Treatment A	XXXXXXX	DDMMYYYY	DDMMYYYY	DDMMYYYY/ DDMMYYYY	DDMMYYYY (XXX)	XXXXXXXXXXXXXXXXXXXXXXXXXX
	. . .					

Etc.

16.2.8: Clinical Laboratory Evaluations
Listing 16.2.8.1: Hematology Parameters - SAF Analysis Set

Treatment Group	Subject Identifier	Visit	Date of Sample (Trial Day)	Comment	Parameter (Unit)	Normal Range	Result	NCI-CTC grade (a)
Treatment A	XXXXXXX	XXXXXXXX	DDMMYYYY (xx)	XXXXXXXXXX	XXXXXXXXXX	XX - XX	XXX*	x/x
					XXXXXXXXXX	XX - XX	XXX L	x
					XXXXXXXXXX	XX - XX	XXX H	
	. . .							

Etc.

(a) NCI-CTCAE version 4.03 for gradeable parameters. For parameters with both low and high grades, the grades are presented as Low/High.

L = value below normal range, H = value above normal range.

* Baseline value.

Note: Baseline is defined as the last non-missing assessment value prior to first dose of trial treatment.

Trial day is defined relative to the date of randomization.

Programming Note: Repeat listing 16.2.8.1 for:

Listing 16.2.8.2: Clinical Chemistry Parameters - SAF Analysis Set

16.2.9: Other Safety Evaluations
Listing 16.2.9.1: Vital Signs - SAF Analysis Set

Treatment Group	Subject Identifier	Visit	Assessment Date (Trial Day)	Blood Pressure (mmHg)		Pulse Rate (beats/min)	Temperature (°C) (Location)	Height (cm)	Weight (kg)
				Systolic	Diastolic				
Treatment A	XXXXXXX	XXXXXXXX	DDMMYYYY (***)	XXX	XXX	XXX	XX (XXXXXX)	XX	XX
		XXXXXXXX	DDMMYYYY (***)	XXX	XXX	XXX	XX (XXXXXX)		
	. . .								

Etc.

~~Note: Trial day is defined relative to the date of randomization.~~

16.2.9: Other Safety Evaluations
Listing 16.2.9.2: Electrocardiogram Data - SAF Analysis Set

Treatment Group	Subject Identifier	Visit	Assessment Date	(Trial Day)	Result	Clinically Significant? (a)
Treatment A	XXXXXXXX	XXXXXXXX	DDMMYYYY	(**)	Normal	
		XXXXXXXX	DDMMYYYY	(**)	Abnormal	No
		XXXXXXXX	DDMMYYYY	(**)	XXXXXXXXXX	xxxxxx
. . .						

Etc.

(a) If result is 'Abnormal'.

~~* Baseline value.~~

~~Note: Baseline is defined as the last non-missing assessment value prior to first dose of trial treatment.~~

~~— Trial day is defined relative to the date of randomization.~~

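### The final-analysis shells contain no urinalysis output and give vital signs as a listing only, so the laboratory and vital-sign safety endpoint is only partly delivered and no specific reason is stated

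*SAP*

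**What the plan says.** Protocol Section 8.3.3 names as a safety endpoint: "Treatment-emergent changes in clinical laboratory measures, ECGs, and vital signs from baseline up to Week 116". The safety paragraph of Section 8.5.3 says how two parts of it will be shown. For continuous data: "Summary statistics will be used to present changes from baseline in continuous laboratory and vital sign data". For categorical laboratory data: "Shift tables will be used to present changes in categorical laboratory parameters".

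Urinalysis belongs to the laboratory measures. Table 4 of the protocol lists a dipstick panel that includes protein, with a reflex test described in the footnotes to Tables 1 and 2: "Urine protein:creatinine ratio to be performed if dipstick urinalysis reveals at least 3+ protein". Urine protein also enters eligibility through exclusion criterion 3.

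The SAP addendum was written after the trial was stopped early. Section 5 says that the full planned analyses will not be run, because the limited data could mislead. Section 17 on safety reads in full: "Refer to the IDMC SAP for the safety summaries that will be provided". Section 8.1 sends the reader to Appendix 1 for the shells. There the laboratory outputs are Tables 15.3.5.1 to 15.3.5.4, Figures 15.3.5.5 to 15.3.5.9 and Listings 16.2.8.1 and 16.2.8.2, all for hematology or clinical chemistry. Vital signs have one output, "Listing 16.2.9.1: Vital Signs - SAF Analysis Set". ECG likewise has one listing, 16.2.9.2.

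**The concern.** The protocol schedules urine dipsticks from screening through Safety Follow-up, and the shells for the final report have no place to put the results. This is the last planned analysis: Section 8.1 of the addendum expects no further data after the cut-off, so no later report would fill the gap.

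The adverse-event tables do not close it. Under protocol Section 7.4.1.1, an abnormal laboratory finding is an adverse event only if it comes with signs and symptoms, leads to treatment discontinuation, or is judged medically important. A rise in dipstick protein that meets none of these conditions, in a subject whose serum chemistry does not move, would not be seen in any Appendix 1 output.

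For vital signs the data are shown, but only subject by subject. A reader who wants the mean change in blood pressure by arm, which Section 8.5.3 commits to, would have to build it from a listing with no baseline flag and no change column.

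**Working it through.** No power or alpha calculation is involved. The check compares the protocol's commitments with every shell in Appendix 1, and then counts the scheduled urine tests.

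**Commitment against output**

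| Component | Protocol commitment | Appendix 1 |
|---|---|---|
| Hematology and chemistry | 8.3.3; change summaries and shift tables in 8.5.3 | 4 shift tables, 5 boxplots, 2 listings |
| Urinalysis | 8.3.3 as a laboratory measure (Table 4); shift tables for categorical laboratory parameters in 8.5.3 | 0 tables, 0 figures, 0 listings |
| Vital signs | 8.3.3; change summaries in 8.5.3 | 0 tables, 0 figures, 1 listing, no change column |
| ECG | 8.3.3; no format set in the visible text of 8.5.3 | 0 tables, 0 figures, 1 listing |

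The programming note under Table 15.3.5.2 says that all parameters are reported, then names hematology and chemistry parameters only. The note under Table 15.3.5.4 gives its gradable parameters as examples and asks for all available ones, but again under hematology and biochemistry. Neither note brings in a urine parameter.

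**Scheduled dipsticks for a completer (protocol Tables 1 and 2)**

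- Weeks 2, 4, 8, 12, 16, 20, 24, 32, 36, 40, 48, 52: 12
- Weeks 60, 64, 68, 76, 84, 88, 92, 100, 104: 9
- Safety Follow-up, 4 and 12 weeks after the last visit: 2
- Post-baseline total: 12 + 9 + 2 = 23. Screening and Day 1 bring it to 25. An early termination visit, where one occurs, has its own.

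**Adverse-event window against the urine schedule**

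The TEAE tables count events starting up to 28 days after the last dose. For a completer the last dose is at Week 100, so the window closes at Week 100 + 4 = Week 104. The two follow-up dipsticks fall at Weeks 104 + 4 = 108 and 104 + 12 = 116, which is 8 and 16 weeks after the last dose. An event first reported from those visits would be in Listing 16.2.7.1 (all adverse events) but not in the by-arm TEAE tables. The endpoint in 8.3.3 runs to Week 116.

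**Is the omission explained?**

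Section 10 of the addendum explains item by item why the ITT, per-protocol, PK and pharmacogenetic sets and the subgroups are dropped. Section 9 refers to the later sections for changes. Section 17 states none. The general reason in Section 5, unreliable conclusions from limited data, does not separate safety from efficacy: Section 16 keeps descriptive summaries of observed value and change for FVC, DLCO, mRSS, the questionnaires and other efficacy measures.

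**The case against.** The strongest case for the addendum is that the reduction is declared. The trial stopped early, the report is abbreviated, and listing vital signs and ECG by subject instead of tabulating them is defensible when arms are small. That carries some weight for vital signs. It carries little for urinalysis, which has not even a listing.

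A reader might go further than the documents allow in five ways.

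- *That the safety endpoint is not delivered.* It is delivered in part: hematology and chemistry are tabulated by arm, and vital signs and ECG are listed.
- *That a renal signal short of an adverse event cannot be seen by arm.* The chemistry shift tables include creatinine, urea, albumin and total protein, and Table 15.2.2.4 counts scleroderma renal crisis by arm. The blind spot is narrower.
- *That a promised ECG summary is missing.* The visible text of Section 8.5.3 promises none.
- *That the protocol flags urine protein as a drug risk.* Section 6.5.4 speaks of "compounds with anti-integrin activity and antiangiogenic potential" but mentions neither kidney nor urine protein in its visible text. Exclusion criterion 3 is an eligibility rule.
- *That urine protein is never reported anywhere.* Section 17 defers to the IDMC SAP, and Appendix 1 embeds a contents file; neither was available. A urinalysis output defined there cannot be ruled out. It is unlikely, since Appendix 1 is presented as combining the IDMC outputs with those new for the final analysis.

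**Conclusion.** The point holds in a limited form. Appendix 1 has no urinalysis output of any kind, and the vital-sign change summaries committed to in protocol Section 8.5.3 have no shell. The endpoint in Section 8.3.3 is therefore only partly delivered, and the addendum gives no specific reason.

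The loss is proteinuria that was not reported as an adverse event and did not show in serum chemistry. Up to 23 scheduled post-baseline dipsticks per completer have no place in the shells. That count is an upper figure for scheduled visits, because subjects stopped early have fewer, and it does not measure any missed signal. The size of a possible signal cannot be estimated from these documents.

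The conclusion assumes that Appendix 1 is the full output set, as its own text suggests. It would change if the IDMC SAP or the embedded contents file defined a urinalysis output. This is a modest gap between protocol and reporting, worth closing because closing it is cheap.

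**What to change.** Add three outputs to Appendix 1, all on the SAF set and by treatment group:

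1. A listing of urinalysis and protein:creatinine results with a baseline flag, using the layout of Listing 16.2.8.1.
2. A shift table of dipstick protein from baseline to the highest post-baseline category through the end of Safety Follow-up. The layout of Table 15.3.5.3 fits, with dipstick categories in place of toxicity grades. The period should be stated, because the companion shells 15.3.5.1 and 15.3.5.2 stop at the worst on-treatment value.
3. A by-visit summary of observed value and change from baseline for vital signs, using the layout of Table 15.2.1.1.

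An ECG shift table is optional. If any of the three is deliberately left out, Sections 9 and 17 should record it as a change from protocol Sections 8.3.3 and 8.5.3, with the reason.

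The cost is a few extra outputs with small numbers per arm, which call for descriptive reading only. The tests are already in the protocol schedule, and Section 7.4.3 has all laboratory parameters other than urine pregnancy tests analyzed centrally, so there should be no burden on sites or subjects.
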